- Study using stored specimens/tissue
- Study using stored medical records
- Others.....

A.7 Is study single center or multicenter

- Single center
- Multicenter (within Nepal)
Please specify the study sites
- Multicenter (International)
Please specify the study sites

Note: NHRC Approval is compulsory for Ph. D/ International Study/ International Collaboration/ Multicenter & Clinical Trial Study.

A.8 Summary of the proposed research protocol (within 200 words)

Cholangiocarcinoma (CCA) or a bile duct cancer is regarded as the second most frequent type of primary liver cancer which is diagnosed in the late decades of life with fatal outcomes. Its risk factors include primary sclerosing cholangitis, hepatitis, smoking, alcohol, obesity, inflammatory bowel disease, cirrhosis, etc. As it is a fatal disease with late diagnosis, knowing the risk factors and its occurrence rate will be helpful to design interventions based on the evidence. It is also important for the early treatment and increased survival rate of patients. It is a quantitative observational type of study. The objective of this study is to collect the clinico-demographic profile of the patients with cholangiocarcinoma undergoing Endoscopic Retrograde Cholangiopancreatography (ERCP) in Dhulikhel Hospital. Self- structured Questionnaire will be used as a research tool for data collection based on literature review. This kind of research is crucial to widen the knowledge in prevention of the morbidity and mortality due to cholangiocarcinoma. Dhulikhel Hospital is a pioneer tertiary care center in Nepal for ERCP, where cases are from different parts of Nepal and their medical records will be reviewed to generate the

evidence of the clinico-demographic profile of the patient with cholangiocarcinoma undergoing ERCP.

A.9 Source of Funding/Sponsor

Non Funded

A.11 Declaration of Co-I

None

B. DETAIL OF THE STUDY

B.1. Background:

Bile is a complex aqueous secretion that originates from hepatocytes of liver then stored and concentrated in gallbladder or is delivered directly to the intestinal lumen whose function is to break down fats and help the body to remove excretory products.¹ Bile duct is a tube which connects gallbladder and liver to the small intestine to allow flow of bile into the small intestine.¹ Cholangiocarcinoma (CCA) is an epithelial cell malignancy of biliary tree that arises from varying locations.² Of three types i.e Extra hepatic, Hilar and Intra hepatic cholangiocarcinoma, Extra hepatic is the most common and most treatable form of cholangiocarcinoma.³⁻⁵ Risk factors include primary sclerosing cholangitis, hepatitis, smoking, alcohol, obesity, inflammatory bowel disease, cirrhosis, host genetic polymorphisms, etc.⁶

Discussing the data of cholangiocarcinoma, these are most common in Southeast and East Asia due to the prevalence of parasitic infection in those particular areas as it is one of the important causes of cholangiocarcinoma.⁷ *Ophisthorchis Viverrini* and *Clonorchis sinensis* are the hepatobiliary flukes mainly associated with CCA in Southeast Asia.⁶ A study done in the United States stated the continued increment in incidence of cholangiocarcinoma from 2001-2017 with greater increase in intrahepatic CCA than extrahepatic CCA.⁸ Different liver flukes are also associated with cholangiocarcinoma in countries like Vietnam, Thailand, Korea, China, Vietnam, etc.⁷

Accounting for about 2% of all malignancies, CCA is considered as a rare malignancy.⁹ It rarely occurs before the fourth decade of life with a wide variation of incidence rates in different geographical regions that reflect the distribution of risk factors, both environmental and genetic.^{9,10} Hence it is known as the disease with late diagnosis and fatal outcome.¹¹ This form of cancer is prevalent in males compared to females and it is found to affect people in their fifth to seventh decade of life.¹¹ According to the American Cancer Society (2023), about 41,420 cases of liver and intra hepatic cancer are estimated including both sexes among which 29,380 deaths are reckoned.¹² CCA is regarded as the second most frequent type of primary liver cancer.¹³ Risk factors related to CCA may vary within different geographical variations.¹⁴ In case of hepatobiliary cancers, CCA accounts for about 20% of death whereas it constitutes 13% of total cancer mortality.¹⁵ As it is not more frequently diagnosed worldwide, it is also regarded as an orphan cancer.¹⁶

The treatment choice of CCA either surgical or radiological, is dependent on different factors such as anatomical position, lymph node and vascular invasion, metastatic condition, etc.^{13,16} In case of chemotherapy, combination of gemcitabine and cisplatin has been considered as a standard chemotherapy regimen as the combination of both of them has been shown overall survival rate of 3.6 months as compared to gemcitabine alone.¹⁷ Patients are usually diagnosed at older age and further it is made worse by symptoms such as pruritus, jaundice, ascites, etc.¹⁸ There has been limited information on the application of autoantibodies (AABs) as biomarkers in case of primary liver tumors such as CCA so far.¹⁹ However, carbohydrate antigen 19-9 (CA19-9) and carcinoembryonic antigen (CEA) were the most commonly studied biomarkers.¹⁹

B.2. Statement of the problem/ rationale/ need of the study:

Studies have shown that the death rate from Cancer is increasing globally, especially in low and middle income countries.^{19,20} Incidence of CCA is increasing in western countries during the last decades and increasing tremendously in Asian countries as well.^{10,19,20} The number of CCA raised from 1720 in 2010 to 2161 in 2013 in England.²¹ The highest incidence of CCA has been reported in northeast Thailand.²²

Nepal being an Asian country is also in the region to have increased cases of cholangiocarcinoma and need rigorous scientific studies to generate evidence to prepare interventions on its prevention and treatment. Cholangiocarcinoma being the major contributing factor for the death of the humans, this needs early diagnosis and treatment system to intrude the increasing mortality and morbidities. Studies should be conducted in its risk factors, disease status, occurrence and other factors so that such studies are considered to estimate the prevention and management of such deadly diseases.

The studies on this sector is in dearth and is in great need of the involvement of academia, medical centers and different institutions. Such studies will provide evidence to plan several interventions for its better and efficient prevention and treatment option.

B.3. Research hypothesis (if applicable):

NA

B.4. Objectives of the research:

General objective (s)

The aim of the study is to assess the clinico-demographic profile of the patient with cholangio-carcinoma undergoing ERCP in Dhulikhel Hospital.

Specific objective(s):

This study holds the objective,

- To identify clinical profile of the patient with cholangio-carcinoma undergoing ERCP
- To describe the demographic profile of the patient with cholangio-carcinoma undergoing ERCP
- To measure the outcome of ERCP procedure in them.
- To identify the association between demographic variable and clinical presentation of the patient with cholangio-carcinoma undergoing ERCP

B.5. Study site and justification:

The study will be conducted in the Endoscopy unit of the Internal medicine department of Dhulikhel Hospital. This hospital has provided services to more than 50 out of 75 districts of the country. It provides services to about 2.7 million people from Kavrepalanchowk, Sindhupalchowk, Dolakha, Lalitpur, Kathmandu, Sindhuli, Ramechhap and other surrounding districts per-year. In Nepal ERCP procedure has been limited to very few Tertiary centers and Dhulikhel Hospital is the pioneer institute to provide the ERCP procedure (since 2011) in the nation. This procedure is mainly performed for the indication of choledocolithiasis, obstructive Jaundice, acute biliary pancreatitis, cholangiocarcinoma, etc. In 2019 only, a total of 1352 patients had undergone ERCP in Dhulikhel Hospital as per the monthly ERCP report book obtained from the Department of Endoscopy of Dhulikhel Hospital.

B6. METHODS/ METHODOLOGY:

B.6.1 Research Methods (Cross in the appropriate box)

a) Qualitative Research Quantitative Research c) Mixed Research

B.6.2. Study design:

This is a quantitative, retrospective, descriptive cross-sectional observational study.. The outcome and the exposure will be measured at the same time as a snapshot.

B.6.3. Study Variables

The study variables will be the socio-demographic variables and the clinical details of the study participants.

B.6.4. Expected outcomes of the research

The expected outcome of the research is to present a clinical finding of this under studied clinical area in Nepal. Furthermore, this will be a reference for the future researchers to conduct further studies on this sector to enhance the prevention, management and the treatment services.

B.7 STUDY POPULATION AND SAMPLE

B.7.1. Participants/ study population:

Patients with cholangiocarcinoma who had undergone ERCP in Endoscopic Department of Dhulikhel Hospital. The patient's information will be obtained from patients' medical records from the outpatient and inpatient department of Dhulikhel Hospital. Thus, the person will not be contacted directly for the data collection.

B.7.2 Selection criteria:

Inclusion criteria:

- All the participants with cholangiocarcinoma had undergone ERCP
- above 18 years of age.

Exclusion criteria:

- ERCP failed cases

B.7.3. Sampling method/ technique:

We will do purposive sampling from the eligible list obtained from the medical records.

B.7.4. Sampling Unit:

The sampling unit is the patient with cholangiocarcinoma who had undergone ERCP.

B.7.5 Sample size determination:

All the eligible cases listed in the medical record of Dhulikhel Hospital from January 2017 to January 2023. Hospital records showed approximately 75 cases of cholangiocarcinoma per year. So, we will conduct a total population sampling with an estimated sample size of 375.

B.8. Procedure:

First of all, the researcher will get formal approval for data collection in the institution.

- After ethical clearance, data will be collected through a case sheet of the patient and record of ERCP procedure at the department using prepared Per forma.
- Data of procedure outcome will be collected via call to the patient. Before collecting information from the respondent, they will be informed about the objective of the study and will be assured of privacy and volunteering participation.

B.8.1. Data Collection Tools/ Measures:

- Clinical Proforma will be used to collect data
 - Part I: Socio-Demographic information of patient
 - Part II: Information related to Clinical profile of patient
 - Part III: outcome of ERCP procedure
- The data will then be entered into Microsoft Excel for further data management.

B.8.2. Pretesting

The proforma will be pretested entering about 10 cases so that we can further modify the proforma.

B.8.3. Validity and Reliability of tool

The tool will be the proforma and this will be based on other literatures and as per the experts suggestion. Indeed, the principal investigator is the physician (expert) to perform this procedure in Nepal and other team members have some kind of exposure in this sector.

B.9. Plan for specimen/data management:

(a) Data Processing

- Collected data will be stored in a file to prevent loss or damage.
- Data will be coded and entered in Microsoft Excel Sheet and will be transferred to the Statistical Program for Social Science (SPSS) for further analysis.

(b) Presentation of Data

- Data will be categorized on the basis of research objectives.
- The study will present the descriptive statistics and other details of the variables.

B.10. Plan for data analysis:

B.10. a. SPSS (Statistical Program for Social Science) version 25.0 will be used for descriptive as well as inferential statistics.

B.10. b. Statistical tests: Descriptive statistics (mean, frequency, standard deviation and percentage) will be applied. For inferential statistics, Chi-square test will be used for the analysis of the categorical data while, t-test or correlation will be done for the continuous variables.

B.11. Potential Biases:

There may be some confounders that will direct to the bias of the study. The information in the confounders will be collected and if required will be adjusted in the data analysis.

B.12. Limitations of the study:

- This is not a common disease, so the sample size of the eligible participants is limited.
- The retrospective study nature of this study may not allow us to incorporate as much information as we are seeking. However, future research may address these issues.

B.13. Plan for supervision and monitoring:

- Data will be collected by the co-authors
- Supervision and monitoring will be done by Principal Investigator and the research team

B.14. Plan for dissemination of the research:

The research will be disseminated to:

- Conferences
- Publication in one of the index peer review journal

B.15. DATA AND SPECIMEN BANKING AND/OR SHARING

B15.1 Management of specimen/data archiving or left-over

NA

B15.2 Specimen/data sharing plan

NA

C. ETHICAL CONSIDERATION

10.1. Ethical issues	Yes/ No	Justification if yes
a. Are human participants included in the study?	Yes	The study aims to determine the clinico-demographic profile of the patients with cholangiocarcinoma undergoing ERCP in Dhulikhel Hospital. But we will not have face to face interaction, as all the information will be obtained from the medical records.
b. Are vulnerable members of the population required for this research? (includes age under 18, pregnant women etc)	No	
c. Are there any risks involved for the participants? If yes, identify clearly what are the expected risks for the human participants in the research and provide a justification for these risks.	No	
d. Are there any benefits involved for the participants? If yes, identify clearly what are the expected benefits for the participants.	No	

C1. SIGNIFICANCE OF THE STUDY

- The study can reveal some risk factors associated with the particular disease i.e Cholangiocarcinoma. Thus, it can be regarded as a baseline study for conducting any intervention.
- It can also be used as a reference for future study purposes in similar types of study.

C2. BALANCE OF RISK AND BENEFIT

C2.1 Risk of the study and Preventive and alleviative measures for risk

C2.1. Risk management:	
Potential risks identified	Proposed measures to mitigate risks
1. No direct risk/harm to the study participants as medical records will be reviewed primarily for patient data collection.	NA
2. Information on the patient's current status will be gathered via telephone interview (only for the feasible cases) where they may have to spare a few minutes for the data, however, this will take only a few minutes.	Verbal consent will be taken and all the information will be provided to the participants if the interaction is required.

C2.3 Benefits of the study

The study will be helpful to the future researcher to base on this and plan further studies so that we can enhance the prevention and treatment processes.

C3. CONSIDERATION FOR VULNERABLE RESEARCH PARTICIPANTS

Check whether your study involves any of the following vulnerable research participants.

- Prisoners
- Pregnant women
- Mentally ill persons
- Cancer or terminally ill patients
- Neonates/infants/children (aged <18)
- HIV/AIDS patients
- Institutionalized persons e.g. military, students, etc.
- Others (please specify).....

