PART 1: SOCIO-DEMOGRAPHIC CHARACTERISTICS

1. Age (in completed years).....

2. Gender:

Male Female Others (specify).....

3. Ethnicity

- a. Brahmin/chhetri
- b. Newar
- c. Mongolian
- d. Dalit
- e. Terai region
- f.

4. Occupation

- a. Agriculture
- b. Service
- c. Labor
- d. House maker
- e. Student

5. Food habit

- a. Vegetarian
- b. Non-Vegetarian

6. Smoking Habit

- a. Yes
- b. No

7. Alcohol Intake

- a. Non-alcoholic
- b. Moderate
- c. Significant

Part 2: Information related to Clinical profile of the patient

1. Mode of presentation

- a. Cholangitis
- b. Obstructive Jaundice
- c. Non-icteric Cholestasis

2. Comorbidity

- a. Yes
- b. No

3. Symptoms

- a. Itching
- b. Abdominal Pain
- c. Asymptomatic Jaundice
- d. Anorexia
- e. Weight loss

4. Investigations

- a. USG
- b. CT Scan
- c. MRI
- d. MRCP
- e. EUS

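### The proforma records comorbidity only as Yes/No, so of the seven risk factors named in A.8 only smoking and alcohol can be reported separately from the form as written

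*Combined protocol and SAP*

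**What the plan says.** A.8 introduces the disease with a list of causes: "Its risk factors include primary sclerosing cholangitis, hepatitis, smoking, alcohol, obesity, inflammatory bowel disease, cirrhosis, etc". It then says that "knowing the risk factors and its occurrence rate will be helpful to design interventions". B.1 repeats the seven factors, adds host genetic polymorphisms, and discusses liver flukes, which "are the hepatobiliary flukes mainly associated with CCA in Southeast Asia". B.2 makes a general call for research: "Studies should be conducted in its risk factors, disease status, occurrence and other factors". C1 (Significance of the study) says that this study can reveal some risk factors for the disease.

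B.4 sets four specific objectives: clinical profile, demographic profile, outcome of ERCP, and association between demographic variables and clinical presentation.

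On the proforma, Part 1 contains "6. Smoking Habit" (Yes/No) and "7. Alcohol Intake" (three levels). Under "Part 2: Information related to Clinical profile of the patient" there is one item for coexisting disease, "2. Comorbidity", answered Yes or No. B.8.2 provides for a pretest on about 10 cases, after which the form may be changed.

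**The concern.** The background rests on a set of named conditions, and the form cannot show which of them a patient had. A Yes entered for cirrhosis and a Yes entered for, say, hypertension receive the same code, and no later analysis can separate them. The item also lacks a definition of comorbidity, so whether obesity counts is left to the person abstracting the chart. It has no option for not recorded, so an undocumented condition is likely to be entered as No.

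At stake is how useful the clinical profile will be. The comorbidity item would give one percentage covering unlike conditions. A reader of C1 would expect some account of how often known risk factors occur in this Nepalese series, and would get it for smoking and alcohol only.

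**Working it through.** The check is a count of data fields. The plan states no figure on this point to reproduce, and no sample-size or power formula applies.

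**Inputs.** The seven factors come from A.8. The fields are all the items in Parts 1, 2 and 3 of the proforma.

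| Factor named in A.8 | Own field on the proforma? | Nearest item |
|---|---|---|
| Smoking | Yes | Part 1, item 6 (Yes/No) |
| Alcohol | Yes | Part 1, item 7 (three levels) |
| Primary sclerosing cholangitis | No | Part 2, item 2 (comorbidity Yes/No) |
| Hepatitis | No | Comorbidity Yes/No; the laboratory list has no hepatitis serology |
| Cirrhosis | No | Comorbidity Yes/No |
| Inflammatory bowel disease | No | Comorbidity Yes/No |
| Obesity | No | Comorbidity Yes/No at most; no height, weight or BMI item, and weight loss appears only as a symptom |

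**Count.** 7 named − 2 with a field = 5 without one. The laboratory item covers total and direct bilirubin, ALP, GGT, AST, ALT, PT and INR, and none of these identifies any of the five. Liver-fluke infection, raised in B.1, has no field either.

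**Could a write-in line have been lost when the PDF was read?** This is unlikely. The dotted specify line survives for gender, as do the blanks for age and for each laboratory value. EUS FNA, brush cytology and intraductal biopsy all keep their If Yes follow-up. Comorbidity has neither.

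**What a percentage from improved boxes would mean.** Let N be all patients, Y those with the factor documented, and M those for whom it is not recorded. If documented entries are correct, the proportion with the factor lies between Y/N and (Y + M)/N. Y/N is therefore a lower bound, and the width of the uncertainty from non-recording is M/N. The documents give no figure for M.

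**The case against.** The strongest reply is that nothing the plan commits to is broken. Risk factors are not among the four specific objectives in B.4, and A.8 itself describes the aim as a clinico-demographic profile. The A.8 and B.2 sentences explain why the topic matters and do not promise a result. Only C1 speaks of this study's output, and it says that the study can reveal some factors, which smoking and alcohol satisfy in part. All of this stands.

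A second reply is that the form is provisional. B.8.2 allows it to be changed, B.11 says that information on confounders will be collected, and B.12 admits that a retrospective study may not supply everything sought. This stands only in part, because none of these sections names the missing conditions. A pretest of about 10 charts may contain no patient with an uncommon one, so it may not expose the gap.

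Some stronger readings are tempting, and the documents do not support them:

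- **That no risk-factor information can be reported.** Smoking and alcohol can be.
- **That chart review is the only chance to record these facts.** The source is existing medical records, and nothing says that they cannot be reopened, though that would mean a second abstraction.
- **That the study is discarding good precision.** With 375 patients, 1.96 × √(p(1 − p)/375) gives 2.2 percentage points at p = 5% and 3.0 at p = 10%. Both prevalences are assumptions found nowhere in the documents, and the formula takes every factor to be recorded in all 375 charts. The 375 is itself unsettled: B.7.5 gives about 75 cases a year from January 2017 to January 2023, and 75 × 6 = 450, while 375 = 75 × 5.
- **That liver flukes are as clear an omission as the other five.** B.1 ties them to Southeast Asia and to listed countries that do not include Nepal.
- **That adding the fields would show what causes the disease.** A series made up only of cases gives frequencies among patients, not associations with getting the disease.

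**Conclusion.** The point holds as a limitation of the form. Of the seven risk factors in A.8, two can be reported from the proforma as written, and five cannot be told apart from any other comorbidity. This weakens the first B.4 objective (clinical profile) and confines the C1 statement to smoking and alcohol. It invalidates no planned test and no other specific objective. It is a cheap improvement to make before abstraction, not a defect in the design.

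The conclusion rests on the printed form being complete and being used unchanged. It does not depend on the final number of patients or on any assumed prevalence.

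**What to change.** Before abstraction begins, as part of the B.8.2 pretest, replace Part 2, item 2 with separate Yes / No / Not recorded boxes for:

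- primary sclerosing cholangitis
- hepatitis
- cirrhosis
- inflammatory bowel disease
- obesity
- other comorbidity (specify)

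A box for liver-fluke infection is optional.

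Report each factor as a percentage of all patients, with the not-recorded share beside it. State that the percentage is a lower bound, and attach no claim of precision. If the boxes are not added, reword C1 so that it refers only to smoking and alcohol.

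The cost is a few more fields per chart from the same records. The main drawback is that some factors will often be not recorded, so their percentages may say little.

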5. EUS FNA

- a) Yes
- b) No

6. If Yes

- 1) Positive
- 2) Negative

7. Brush cytology

- a) Yes
- b) No

8. If Yes

- 1) Positive
- 2) Negative

9. Intra ductal biopsy

a) Yes

b) No

10. If Yes

- 1) Positive
- 2) Negative

11. Surgical operability

- a. Operable
- b. Non-operable
- c. Unknown

12. Lab reports

- a) Total bilirubin.....
- b) Direct bilirubin.....
- c) ALP.....
- d) GGT.....
- e) AST.....
- f) ALT.....
- g) PT.....
- h) INR.....

13. Type of growth

- a. Distal
- b. Hilar

1) Bismuth-I

2) Bismuth-II

3) Bismuth-III

4) Bismuth-IV

5) Bismuth-V

Part 3. Outcome of ERCP procedure

14. Type of stent used in ERCP:

- a) Plastic stent
- b) Metal stent (SEMS)

15. Outcome of Stenting

- a) Immediate
- b) Failed Stenting
- c) Successful stenting

16. Complications

- a) Perforation
- b) Bleeding
- c) PEP
- d) PEC

17. If PEP done

- 1) Within 2 weeks
- 2) After 2 weeks

18. If PEC done

- 1) Within 2 weeks
- 2) After 2 weeks

19. Restenting

- a) Yes
- b) No
- 1) Within 1 month
- 2) Within 2 month
- 3) Within 3 month

20. Radio- Frequency Ablation

- Yes
- No

21. Survival Rate

- a) < 1 month
- b) 3-6 month
- c) 6 month- 1 year
- d) >1 year

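### Proforma item 13 has no code for intrahepatic or undetermined tumours, although B.1 names the intrahepatic type and B.7.2 sets no limit by tumour site

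*Combined protocol and SAP*

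**What the plan says.** B.1 (Background) divides the disease into types: "Of three types i.e Extra hepatic, Hilar and Intra hepatic cholangiocarcinoma".

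B.7.1 describes the population without reference to site: "Patients with cholangiocarcinoma who had undergone ERCP in Endoscopic Department of Dhulikhel Hospital". B.7.2 has two inclusion criteria, "All the participants with cholangiocarcinoma had undergone ERCP" and "above 18 years of age", and one exclusion, "ERCP failed cases". None of them concerns where the tumour lies.

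The first specific objective in B.4 is "To identify clinical profile of the patient with cholangio-carcinoma undergoing ERCP". Part 2 of the proforma serves that objective. Within it, the item "13. Type of growth" has two codes as printed, Distal and Hilar, the second followed by Bismuth subtypes I to V. It has no intrahepatic, other or unknown code. Item 11 (surgical operability), on the same form, does have an Unknown code.

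B.8.2 provides for a pretest: "The proforma will be pretested entering about 10 cases so that we can further modify the proforma". B.9 and B.10 give no coding rule, missing-data rule or denominator for a tumour that fits neither code of item 13.

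**The concern.** The eligibility rule and the form do not cover the same set of tumours. Patients can enter the study with a tumour that the form cannot describe. No other item records location, so the information is lost at abstraction.

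A blank in item 13 would also be ambiguous. It could mean intrahepatic, site not determined, or simply overlooked, and these could be separated later only by going back to the charts.

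Tumour location is a natural part of a clinical profile. B.1 itself says that treatment choice depends on anatomical position among other factors, and cites a larger rise in intrahepatic than in extrahepatic disease in one country. A report from this form could say nothing about the intrahepatic type. Depending on how the unclassifiable cases are handled, it could also misstate the distal and hilar shares.

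**Working it through.** **1. Types against codes**

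| Type in B.1 | Admitted by B.7.2? | Code in item 13 |
|---|---|---|
| Extrahepatic | Yes | Distal, if that is what the term means; no mapping is given |
| Hilar | Yes | Hilar, with Bismuth subtype |
| Intrahepatic | Yes, not excluded | None |
| Site not determined | Yes, not excluded | None |

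Two of the three named types have a code, and an undetermined site has none.

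**2. Denominator**

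B.7.5 gives about 75 cases a year and an estimated sample of 375. That figure is reproduced by 75 × 5 = 375. The stated window, January 2017 to January 2023, is about six years and gives 75 × 6 = 450. This mismatch is a separate matter and neither supports nor weakens the present point. Both totals are shown below.

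**3. Records without a code**

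Let q be the share of included patients whose tumour is intrahepatic or of undetermined site. The documents give no value, so q is an assumption. The number without a code is q × N.

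| q | N = 375 | N = 450 |
|---|---|---|
| 2% | 7.5, about 8 | 9 |
| 5% | 18.75, about 19 | 22.5, about 23 |
| 10% | 37.5, about 38 | 45 |
| 20% | 75 | 90 |

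**4. Effect on the reported hilar share**

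As a further assumption, let the remaining tumours split evenly between distal and hilar. The true hilar share of all patients is then h = 0.5 × (1 − q). Three ways of handling the uncoded cases give:

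- blank, with percentages over all included patients: h
- blank, with percentages over completed items only: h / (1 − q) = 50%
- all forced into Hilar: h + q

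| q | Over all patients (true) | Completed items only | All forced into Hilar |
|---|---|---|---|
| 2% | 49.0% | 50.0% | 51.0% |
| 5% | 47.5% | 50.0% | 52.5% |
| 10% | 45.0% | 50.0% | 55.0% |
| 20% | 40.0% | 50.0% | 60.0% |

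Holding the true hilar share at 50% of all patients instead gives 0.50 + q = 52% to 70% if forced and 0.50 / (1 − q) = 51% to 62.5% over completed items. The direction is the same. The first column of the table shows that blanks reported over all patients do not bias the hilar share.

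**5. Could the pretest reveal the gap?**

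Treating the roughly ten pretest cases as independent draws, the chance that none is affected is (1 − q)^10. This is 0.95^10 ≈ 60% at q = 5% and 0.90^10 ≈ 35% at q = 10%.

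**The case against.** The strongest reply is that the form is written for obstructing ductal tumours treated by stent. The modes of presentation are cholangitis, obstructive jaundice and non-icteric cholestasis. Part 3 is mostly about stent type, stenting outcome and restenting, and failed ERCP is excluded. Intrahepatic tumours may be few in such a series. This stands as a reason to expect a small effect. It does not remove the mismatch, because nothing in B.7 limits the site, and it does not touch the undetermined cases. B.12 accepts that a retrospective review may not yield all the information sought, so undetermined sites are foreseeable.

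Second, a reader might infer that uncoded patients must be dropped from the study or that the type distribution will necessarily be biased. The documents support neither. A blank in one field removes no patient. Bias needs either forced coding or a denominator restricted to completed items, and the plan specifies neither.

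Third, B.1 is a referenced background sentence and not an operational definition, and neither B.6.3 nor B.10 names tumour type as an analysis variable. Other items, such as occupation, also lack a catch-all code. This is fair and limits the weight of the point. Still, item 13 is in the part of the form that serves objective 1, and what it lacks is a type that the protocol itself names.

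Fourth, the form is provisional until the pretest. That is a route to correction, but B.8.2 does not mention this item and about ten cases could easily contain no such tumour.

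**Conclusion.** The point holds as a gap between eligibility and data capture. Used as printed, item 13 cannot record one of the three types named in B.1, nor an undetermined site, although B.7.2 admits both. Such records would be left blank or put in a wrong category, so the tumour-type part of objective 1 cannot show intrahepatic disease.

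The size is unknown. The figure of about 8 to 75 of 375 records rests wholly on an assumed share of 2% to 20%, and the shifts in the hilar share rest also on assumed splits and on how blanks are treated. They show a direction, not an estimate, and the largest of them requires the highest assumed share with every case forced one way. The true effect may be close to nil.

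Nor should a reader infer that the site can always be recovered from imaging. Item 4 lists modalities only, and nothing says what the reports contain. The change is worth making because it is cheap before abstraction, whereas afterwards it would mean re-opening charts.

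**What to change.** Add two codes to item 13, Intrahepatic and Not determined/not recorded. State how Distal relates to the extrahepatic type in B.1, and keep the Bismuth subtypes under Hilar. Add one sentence to B.10: tumour type is reported over all included patients, with the undetermined number shown.

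Alternatively, if only distal and hilar disease is intended, restrict B.7.2 and the objectives accordingly. The Not determined/not recorded code is still needed in that case.

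The cost is two tick boxes and a sentence, or one inclusion phrase and one tick box, made before abstraction starts. The planned revision after the pretest is a convenient moment, but the change should not wait for a pretest case to reveal the gap.
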